#### Table 6–2: Chemistry

Abbreviations: ALT= alanine aminotransferase; AST = aspartate aminotransferase; dL = deciliter; GGT: gamma glutamyltransferase; L = liter; mg = milligram; mmol = millimoles;  $\mu$ g = microgram; U = unit; ULN = upper limit of normal

Note: Marked abnormality criteria are defined by Grade 3 or higher events according to the Common Terminology for Adverse Events (CTCAE), Version 5.0, unless otherwise noted.

The value of eGFR is calculated using the Chronic Kidney Disease Epidemiology Collaboration or CKD-EPI formula (https://qxmd.com/calculate/calculator\_251/egfr-using-ckd-epi) which is eGFR = 141 \* min(Scr/ $\kappa$ , 1) $\alpha$  \* max(Scr/ $\kappa$ , 1)-1.209 \* 0.993Age \* 1.018 [if female]; where Scr is serum creatinine (mg/dL),  $\kappa$  is 0.7 for females and 0.9 for males,  $\alpha$  is -0.329 for females and -0.411 for males, min indicates the minimum of Scr/ $\kappa$  or 1, and max indicates the maximum of Scr/ $\kappa$  or 1. For derivation from values in standard units (umol/L) the  $\kappa$  values are 61.88 for females and 79.56 for males.

Includes CRP and High Sensitivity (HS) CRP. Reference for marked abnormality criteria: Nehring, S.M.; Goyal, A.; Patel, B.C. (2020). StatPearls Publishing, web link: https://www.ncbi.nlm.nih.gov/books/NBK441843/. A moderate elevation of CRP level per referred reference is used for the marked abnormality criteria for RLZ to ensure a change suggestive of inflammatory process is captured. Standard CRP test should be used. In case high sensitivity CRP (hs-CRP) test have been used in any ongoing studies apply same value (>100mg/L) as marked abnormality criteria.

Corrected Calcium (mmol/L) =0.02 \* (40 – Albumin (g/L)) + Calcium (mmol/L).

Immunoglobulin G criterion based on immunodeficiency literature and noted in RLZ study protocols.

Glucose high criterion defined by Grade 3 and higher events according to CTCAE, Version 4.03, June 14, 2010.

#### Table 6–3: Vital Signs

Parameter	Abnormality Criteria
Pulse Rate (beats/minute)	$\leq$ 50 and a decrease from Baseline of $\geq$ 15
	$\geq$ 120 and an increase from Baseline of $\geq$ 15
Systolic Blood Pressure (mmHg)	$\leq 90$ and a decrease from Baseline of $\geq 20$
, ( U ,	$\geq$ 180 and an increase from Baseline of $\geq$ 20
Diastolic Blood Pressure (mmHg)	$\leq$ 50 and a decrease from Baseline of $\geq$ 15
	$\geq$ 105 and an increase from Baseline of $\geq$ 15
Temperature	>101 °F (38.3 °C)
ble 6–4: Electrocardiogram	Mo ions

#### Table 6–4: Electrocardiogram

Parameter	Abnormality Criteria
QT interval (ms)	≥500ms
	≥60ms increase from Baseline
QTc(F) (ms)	≥500ms
	≥60ms increase from Baseline
PR interval (ms)	>200ms
QRS interval (ms)	>100ms
Heart rate (bpm)	<50bpm
in so	>120bpm

Abbreviations: bpm = beats per minute; ms = milliseconds; QTc(F) = Fridericia corrected QT interval;

Note: Treatment-emergent is defined as meeting the criteria at any post-Baseline visit after the first infusion of study medication and within 56-days of the last infusion and not meeting the same criteria during Baseline.

#### Appendix 10: Compliance 6.10

Not applicable. The number of infusions will be recorded as detailed in Section 4.5.1.

#### Appendix 11: Myasthenia Gravis-Activities of Daily Living 6.11

The MG-ADL score comprises 8 items, each with a score of 0 to 3. The total score is obtained by summing the responses to each individual item. Thus, the score ranges from 0 to 24 with a higher score indicating more disability. The MG-ADL testing form is provided in Table 6–5.

In the event of missing data, the following rules will be applied:

tilor

- If 1 or 2 items are not answered, the overall score will be obtained by imputing the missing items with the average score across the remaining items at the specific visit. The imputed value will be rounded to one decimal place
- If more than 2 items are missing the overall score will not be calculated.

Table 6–5: MG-Activities of Daily Living

Grade	0	1	2	3	Score
Talking	Normal	Intermittent slurring or nasal speech	Constant slurring or nasal, but can be understood	Difficult to understand speech	2 utro
Chewing	Normal	Fatigue with solid food	Fatigue with soft food	Gastric tube	SIN 6
Swallowing	Normal	Rare episode of choking	Frequent choking necessitating changes in diet	Gastric tube	
Breathing	Normal	Shortness of breath with exertion	Shortness of breath at rest	Ventillator dependence	
Impairment of ability to brush teeth or comb hair	None	Extra effort, but no rest periods needed.	Rest periods needed	Cannot do one of these functions	
Impairment of ability to arise from a chair	None	Mild, sometimes uses anns	Moderate, always uses arms	Severe, requires assistance	
Double vision	None	but not daily	Daily, but not constant	Constant	
Eyelid droop	None	Occurs out not daily	Daily, but not constant	Constant	
	×	e nt		Total score	

### 6.12 Appendix 12: Impact of the coronavirus disease 2019 (COVID-19) on study data

Missing data is expected to be one of the major implications of the COVID-19 pandemic. The following approaches/strategies will be applied to assess the impact of COVID-19 in this study.

• Added an electronic Case Report Form (eCRF) page "COVID-19 Impact", including impacted visits, impact categories and relationship to COVID-19;

Additional fields were added in protocol deviation specification documents to record protocol deviations relationship to COVID-19.

### 6.13 Appendix 13: AEs of focus for Rozanolixizumab program

The AEOF selection criteria is specified in the Rozimab Safety AEs of Focus document developed by UCB. The purpose of this document is to detail the approach to identifying TEAEs

meeting criteria for AEOF for the Rozanolixizumab (also called RLZ) program.

[figure not shown]
No	Event (also included in Title of TFL output)	Selection criteria
1	Headache (Note: also included in AESM if severe and/or serious)	TEAE with HLGT='Headaches'
2	Possible aseptic meningitis (Note: also included in AESM)	SMQ=' Noninfectious meningitis' narrow search
3	Gastrointestinal disturbances	TEAE with HLT='Gastrointestinal and abdominal pains (excl oral and throat)' or -HLT='Nausea and vomiting symptoms' or HLT='Diarrhoea (excl infective)' or HLT='Gastritis (excl infective)' or PT = 'Abdominal discomfort'
4	Hypersensitivity reactions	SMQ='Hypersensitivity' narrow search
5	Anaphylactic reactions	
 
SMQ='Anaphylactic reaction' and TEAEs that either emerged on the same day as when a study medication injection reaction was received, or that emerged one day after a study medication injection was received, and which fulfill any of the following 3 criteria should be included in the summary table:
 
If a subject reports any TEAE which codes to a PT included in Category A, then the event will be flagged as an anaphylactic reaction.
 
If a subject reports any TEAE which codes to a PT included in Category B AND reports any TEAE which codes to a PT included in Category C, and both TEAEs have the same start date, then both events will be flagged as anaphylactic reactions.
 

90C1	Injection site reactions	3. If a subject reports any TEAE which codes to a PT included in Category D AND reports (either a TEAE which codes to a PT included in Category B OR a TEAE which codes to a PT included in Category C), and both TEAEs have the same start date, then both events will be flagged as anaphylactic reactions.
6	Injection site reactions	TEAE with HLT='Injection site reactions' or HLT='Infusion site reactions' or HLT='Administration site reactions NEC'

[figure not shown]
Following Events are AEOFs for Rozimab for MG studies:

[figure not shown]
No	Event (also included in	Selection criteria
	Title of TFL output)	
7	Infections	TEAE with SOC ="Infections and infestations"
		Note: This was added as a reminder for safety that infections
		are considered as AE of focus and require assessment. No
		programming of this topic is required as TEAEs can be found
		in general AE Tables.
8	Opportunistic infections	TEAEs in MedDRA SMQ = 'Opportunistic infections' narrow
		search
9	Reductions in albumin and	TEAEs with PT='Blood albumin decreased' or PT='Protein albumin ratio' or LLT='Plasma protein abnormal' or
	plasma proteins	PT='Blood albumin decreased' or
		PT='Protein albumin ratio' or
		LLT='Plasma protein abnormal' or
		LL I= Proteins serum plasma low
10	Effects on the kidney	TEAEs in
		SMQ= 'Acute renal failure' narrow search
11	Drug related hepatic	TEAEs in
	disorders	SMQ='Drug related hepatic disorders - comprehensive search'
		narrow and broad search
12	Effect on lipids	TEAEs with
		PT= 'Blood cholesterol increased' or
		PT= 'Low density lipoprotein increased' or
		PT= Blood triglycerides increased' or
		PT= 'Hypercholesterolaemia' or
		PT='Hypertriglyceridaemia' or
		PT= 'Hyperlipidaemia' or
		PT= 'Dyslipidaemia' or
	X	PT='Lipids increased'

[figure not shown]
Hype PT= byslip PT= byslip PT= Lipids.

[figure not shown]

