- 13. Study participant has 12-lead electrocardiogram (ECG) at Screening (Visit 1) with findings considered to be clinically significant upon medical review. The clinical significance of the findings needs to be assessed by the investigator to determine eligibility.
- 14. Study participant has >3.0xULN of any of the following: alanine aminotransferase (ALT), aspartate aminotransferase (AST), or alkaline phosphatase (ALP) at Screening (Visit 1).
 - If participant has >upper limit of normal (ULN) for ALT, AST, or ALP that does not meet the exclusion limit at Screening (Visit 1), repeat the tests, if possible, before dosing to ensure there is no further ongoing clinically relevant increase.

- For participants with a Baseline result >ULN for ALT, AST, ALP, or total bilirubin, a
 Baseline diagnosis and/or the cause of any clinically meaningful elevation must be
 recorded in the CRF.
- 15. Study participant has bilirubin >1.5xULN at Screening (Visit 1) (unless confirmed Gilbert's syndrome). If participant has elevations only in total bilirubin, the fractionate bilirubin needs to be checked, to identify possible undiagnosed Gilbert's syndrome (ie, direct bilirubin <35%).
- 16. Current unstable liver or biliary disease, at Screening (Visit 1), per investigator assessment defined by the presence of ascites, encephalopathy, coagulopathy, hypoalbuminemia, esophageal or gastric varices, persistent jaundice, or cirrhosis. NOTE: with exception of stable hepatobiliary conditions (including Gilbert's syndrome, asymptomatic gallstones).
- 17. Presence of Hepatitis B surface antigen (HBsAg) or positive Hepatitis C antibody test result at Screening (Visit 1). Note: a study participant with a positive hepatitis C antibody test due to prior resolved disease can be enrolled only if a confirmatory negative Hepatitis C RNA test is obtained.
- 18. Study participant tests positive for human immunodeficiency virus at Screening (Visit 1).
- 19a. Study participant has active malignant neoplastic disease or history of malignant neoplastic disease within 5 years of study entry before Screening (Visit 1) (except for basal or squamous cell carcinoma of the skin or carcinoma in situ of the uterine cervix that have been definitively treated with standard of care approaches or thymoma that did not require chemotherapy and/or radiotherapy after removal).

Other

20. Study participant has a lifetime history of

as indicated by a positive

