- When an AE/SAE occurs, it is the responsibility of the investigator to review all
 documentation (eg, hospital progress notes, laboratory reports, and diagnostics reports) related
 to the event.
- The investigator will then record all relevant AE/SAE information in the CRF.
- It is **not** acceptable for the investigator to send photocopies of the participant's medical records to UCB in lieu of completion of the UCB AE/SAE CRF page.
- There may be instances when copies of medical records for certain cases are requested by
 UCB. In this case, all participant identifiers, with the exception of the participant number, will
 be redacted on the copies of the medical records before submission to UCB.
- The investigator will attempt to establish a diagnosis of the event based on signs, symptoms, and/or other clinical information. Whenever possible, the diagnosis (not the individual signs/symptoms) will be documented as the AE/SAE.

Assessment of intensity

The investigator will make an assessment of intensity for each AE and SAE reported during the study and assign it to 1 of the following categories:

- Mild: An event that is easily tolerated by the participant, causing minimal discomfort and not interfering with everyday activities.
- Moderate: An event that causes sufficient discomfort and interferes with normal everyday activities.
- Severe: An event that prevents normal everyday activities. An AE that is assessed as severe should not be confused with a SAE. Severe is a category utilized for rating the intensity of an event; and both AEs and SAEs can be assessed as severe.
- An event is defined as 'serious' when it meets at least 1 of the predefined outcomes as described in the definition of a SAE, NOT when it is rated as severe (eg, a severe AE may be either serious or not serious, depending on whether these criteria are also met).

The National Cancer Institute Common Terminology Criteria for Adverse Events (NCI-CTCAE) should be used as a supportive standardization instrument to evaluate AEs and SAEs but the final intensity grading by the investigator must be mild, moderate, or severe.

Assessment of causality

- The investigator is obligated to assess the relationship between study medication and each occurrence of each AE/SAE.
- A "reasonable possibility" of a relationship conveys that there are facts, evidence, and/or arguments to suggest a causal relationship, rather than a relationship cannot be ruled out.

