Listings of all AEs, all non-serious TEAEs, serious TEAEs, permanent withdrawal of IMP due to TEAEs, study participant discontinuation from study due to AEs, AEs leading to death, AESIs, and AESMs will be presented by sequence (if applicable), period (if applicable) and participant for the SS. AE duration will be included in the listings. Hospitalization data will be listed.

Rozanolixizumab treatment-emergent adverse events of focus (TEAEOF) will also be analysed for the SS. TEAEOF are defined in Section 6.13. The number and percentage of study participants who experience each category of the TEAEOF will be summarized. The following summaries will be presented by SOC, HLT and PT:

- TEAEOF (presented also for RSS)
- Serious TEAEOF
- TEAEOF by maximum intensity (mild, moderate and severe)

A by-subject listing of all TEAEOF by category (as listed above) will be provided. Further details related to the statistical analysis of the above mentioned treatment-emergent AEOFs are provided in Section 6.13.

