#### List of Abbroviations

#### Appendix 2: Coding dictionaries 6.2

Adverse events (AEs) and medical histories will be coded using version 24.0 or later of the Medical Dictionary for Regulatory Activities (MedDRA®).

Medications will be coded according to B3 version Sep 2020 or later of the World Health Organization Drug Dictionary (WHODD).

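### SAP 6.13 row 9 identifies reduced albumin by four laboratory-type terms and no diagnosis term, so a TEAE coded to hypoalbuminaemia (assumed to be a separate PT) would be left out of the category

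*SAP*

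**What the plan says.** SAP 6.13 lists the adverse events of focus for the rozanolixizumab programme, with a selection rule for each. Row 9, on reductions in albumin and plasma proteins, reads "TEAEs with PT='Blood albumin decreased' or PT='Protein albumin ratio' or LLT='Plasma protein abnormal' or" and closes with a fourth term, an LLT for low serum or plasma proteins. Row 10 follows. In the text as read from the PDF the first three terms are printed twice; I treat that as an extraction artefact and not as a fault of the plan.

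Row 12, on lipids, is also built from single terms, but it mixes two kinds. Beside laboratory findings such as *Blood cholesterol increased* it lists diagnoses, for example "PT= 'Hypercholesterolaemia' or" and three others.

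SAP 4.5.2 makes each category a reported result: "The number and percentage of study participants who experience each category of the TEAEOF will be summarized". It adds that "A by-subject listing of all TEAEOF by category (as listed above) will be provided". Adverse events "will be coded using version 24.0 or later of the" MedDRA dictionary (SAP 6.2). SAP 6.13 states that the selection criteria come from a sponsor document on AEs of focus for the programme. That document is not part of the material reviewed.

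**The concern.** A category named for low albumin should pick up an adverse event reported as low albumin, whether it is coded as a laboratory finding or as a diagnosis. Row 9 names only the laboratory side. It contains no SMQ, HLT or other grouping level, so a term left off the list is not caught by a wider search within the row. Compare row 10, which uses "SMQ= 'Acute renal failure' narrow search".

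If hypoalbuminaemia is its own PT, a participant whose event is coded there has the event in question but does not count in the category. The reported number and percentage would then be too low, and a reader of the event-of-focus tables could take that as reassurance about albumin. What is at stake is the accuracy of one descriptive safety category.

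**Working it through.** The plan gives no figure to reproduce here. The check compares the two rows term by term and then applies the row 9 rule to a single event.

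**Row 9 (SAP 6.13), distinct terms**
- PT *Blood albumin decreased*: laboratory-type
- PT *Protein albumin ratio*: laboratory-type
- LLT *Plasma protein abnormal*: laboratory-type
- LLT *Proteins serum plasma low*: laboratory-type

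Total: 4 terms, 4 laboratory-type, 0 diagnosis.

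**Row 12 (SAP 6.13), distinct terms**
- Laboratory-type PTs: *Blood cholesterol increased*, *Low density lipoprotein increased*, *Blood triglycerides increased*, *Lipids increased*
- Diagnosis PTs: *Hypercholesterolaemia*, *Hypertriglyceridaemia*, *Hyperlipidaemia*, *Dyslipidaemia*

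Total: 8 terms, 4 laboratory-type, 4 diagnosis. Two pairs match directly: raised blood cholesterol with hypercholesterolaemia, and raised blood triglycerides with hypertriglyceridaemia. In each pair the laboratory finding and the diagnosis are both named as PTs.

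**Applying the row 9 rule.** Take a TEAE with PT hypoalbuminaemia.
1. Is the PT *Blood albumin decreased*? No, under the assumption that the two PTs are separate.
2. Is the PT *Protein albumin ratio*? No.
3. Is the LLT *Plasma protein abnormal* or *Proteins serum plasma low*? No, if the event was coded to an LLT for hypoalbuminaemia.

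No condition is met, so the event is not selected. If hypoalbuminaemia is instead an LLT under *Blood albumin decreased*, step 1 is met, the event is selected and the gap is zero.

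**Outputs affected (SAP 4.5.2).** TEAEOF for the SS, TEAEOF for the RSS, serious TEAEOF, and TEAEOF by maximum intensity: 4 tables. Adding the by-subject listing gives 1 category in 4 tables and 1 listing.

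**Scale of one missed participant.** The number of missed events cannot be derived from the documents. For illustration, at the planned minimum of 30 randomised participants (Protocol 4.1 and 9.9), one missed participant lowers the category by 1/30 = 3.3 percentage points. With a larger denominator the effect is smaller.

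**The case against.** The strongest reply is that the defect depends on a dictionary fact that neither document contains. Whether hypoalbuminaemia is a separate PT is a yes-or-no matter, and row 12 shows only how certain lipid terms are placed. This stands as a limit on confidence. It does not remove the point: the absence of any diagnosis term from row 9 needs no assumption, and the matched pairs in row 12 are evidence from within the SAP that the assumption is reasonable.

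Second, the text of row 9 is damaged in extraction, so a term might have been lost. The last entry carries no connecting *or* and row 10 follows, which suggests the list is complete. The sponsor can settle this from the source file.

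Third, the list belongs to the programme, and a study-specific change would depart from it. The SAP version history shows an edit to 6.13 made for alignment with the programme SAP. This is a fair cost, and it is why the present count should be kept beside the new one.

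Some stronger readings are tempting and should not be drawn:
- A reader might infer that the protocol directs sites to report hypoalbuminaemia. Protocol 10.3 (Appendix 3) says "Whenever possible, the diagnosis (not the individual signs/symptoms) will be documented as the AE/SAE", but that prefers a diagnosis over signs and symptoms. Protocol 8.2.8 sends clinically relevant laboratory changes to the AE section, which suits laboratory-type terms. The protocol's own use of the word, in "ascites, encephalopathy, coagulopathy, hypoalbuminemia, esophageal or gastric varices" (5.2, exclusion criterion 16), describes unstable liver disease and says nothing about AE coding.
- A reader might infer that row 9 is an outlier because most rows use a grouping level. That count is weak support: row 7 is a reminder that calls for no programming, and row 5 applies PT-category rules on top of its SMQ.
- A reader might infer that further diagnosis terms for low plasma protein are also missing. No such term appears in either document.

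**Conclusion.** The point holds as a minor gap in a stated selection rule. Row 9 has 0 diagnosis terms out of 4 where row 12 has 4 out of 8. On the assumption that hypoalbuminaemia is a separate PT in the MedDRA version used, a TEAE coded to it falls outside the category named for low albumin, and that category could be undercounted. Without the assumption there is no gap. Nothing in the documents shows that an event has been or will be missed.

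It would also be wrong to infer that low albumin goes unreported. Under SAP 4.5.2 such events appear by PT in the general TEAE tables and in the listing of all AEs. SAP 4.5.3.1.1 covers albumin through the chemistry summaries, the shift tables and a plot of mean values, and SAP 6.9 sets a marked-abnormality limit of below 20 g/L. These outputs do not correct the category count, but they keep the consequence small. No primary or secondary endpoint is affected. Confidence is medium because of the dictionary assumption and the unseen programme document.

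**What to change.** Check the status of hypoalbuminaemia in the MedDRA version in use. If it is a PT separate from *Blood albumin decreased*, add it to SAP 6.13 row 9. In the TEAEOF tables, footnote the count from the four terms now listed, so that results remain comparable with other studies in the programme. If the check shows that it already falls under a listed PT, no change is needed.

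The cost is one search term in one SAP row, the matching program line and a footnote. No new data are required. The one drawback, a small departure from the programme list, is covered by the footnoted count.

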## 6.14 Appendix 14: Self-Injection Assessment Questionnaire

[figure not shown]

[figure not shown]

[figure not shown]

#### Appendix 15: Tuberculosis Questionnaire 6.15

Rozanolixizumab

" " Biominal of the service of the s

